Sponsor	The sponsor is the party that commissions the organisation or performance of the research, for example a pharmaceutical company, academic hospital, scientific organisation or investigator. A party that provides funding for a study but does not commission it is not regarded as the sponsor, but referred to as a subsidising party.
SUSAR	Suspected Unexpected Serious Adverse Reaction
TKA/THA	Total Knee Arthroplasty/Total Hip Arthroplasty
Wbp	Personal Data Protection Act (in Dutch: Wet Bescherming Persoonsgegevens)
WMO	Medical Research Involving Human Subjects Act (in Dutch: Wet Medisch-wetenschappelijk Onderzoek met mensen)

SUMMARY

Rationale: Persistent wound leakage after primary TKA/THA is associated with a Prosthetic Joint Infection (PJI). PJI is a serious complication of TKA/THA (2% overall incidence). PJI has major implications for a patient's quality of life and can need revision surgery. Revision surgery for PJI within one year after TKA/THA is necessary in at least 200 patients annually (0.4% of all patients). The costs involved are high (\pm € 30,000).

Persistent wound leakage can be treated both by means of nonsurgical- or surgical treatment. Both are currently applied as usual care. Nonsurgical treatment consists of bed rest, bandages, antibiotics. Surgical treatment consists of debridement, antibiotics and implant retention (DAIR) on days 8-11 postoperative. The rationale for an early treatment of wound leakage is, that in case a PJI is present, adequate surgical and antibiotic treatment as early as possible is strongly associated with prosthesis survival. The dilemma is that not all postoperative prolonged wound leakages are a proxy for a PJI, wound leakage may also be a risk to acquire a PJI. Nonsurgical treatment is aimed at rest to help primary wound healing in order to prevent a PJI. So far the literature shows no evidence for the superiority of surgical over nonsurgical intervention.

Objective: To determine clinical and cost effectiveness and impact on disease-specific and general health-related quality of life of surgical intervention (DAIR on day 10) versus nonsurgical treatment in patients with persistent wound leakage. Primary endpoint will be revision surgery for PJI up to one year.

Study design: A multicenter randomized controlled trial comparing surgical with nonsurgical treatment in case of persistent wound leakage after primary TKA/THA.

Study population: Patients aged 18 or older after primary TKA/THA surgery with a persistent wound leakage at day 9 are eligible for participation in the study.

Intervention (if applicable): Nonsurgical treatment consists of bed rest, bandages, and wound care. Surgical treatment consists of DAIR on day 10. DAIR is meant to clean the prosthesis and the wound in order to conquer the possibility of infection.

Main study parameters/endpoints: The clinical and cost effectiveness of surgical intervention (DAIR day 10) versus nonsurgical treatment in patients with wound leakage after TKA/THA.

Nature and extent of the burden and risks associated with participation, benefit and group relatedness: The goal of the study is to compare two standard clinical policies, which are currently both used as usual care in the Netherlands depending on the physician's or hospital's preference. The patients in our trial will be subjected to one of these policies. It is therefore not plausible that participation will lead to an increased health risk. There is no clear evidence for either treatment regimen. No extra hospital visits are required. The burden of DAIR consists of surgery on day 10. The prostheses is cleaned and it takes 1-1.5 hours. It's as such a safe procedure.

1. INTRODUCTION AND RATIONALE

Total Knee Arthroplasty/Total Hip Arthroplasty (TKA/THA) are highly successful procedures in patients suffering from end-stage osteoarthritis (OA), and results in improvement of joint function and quality of life, and pain relief. These procedures are amongst the most reliable and cost-effective surgical procedures, with more than 50,000 prostheses implanted every year in the Netherlands [LROI 2014]. Due to the aging population it is expected that these numbers will significantly increase in the coming decades. Woundleakage after TKA/THA can be a postoperative problem. Wound leakage is associated with prosthetic joint infection (PJI) which is considered a serious postoperative complication. In this study a comparison is made of the clinical and cost effectiveness of a surgical and non-surgical treatment strategy against persistent wound leakage after primary TKA/THA.

Persistent wound leakage (any wound leakage on or after day 5) after a primary THA/TKA is associated with PJI [Maathuis 2009]. In theory, this might be induced in the postoperative phase by an inflammatory response. The dilemma is whether the inflammatory response 1) is part of a normal postoperative healing process in a proinflammatory environment or 2) is a reaction to a minimal load of bacteria which will be resolved by the patients' immune response, or 3) the inflammatory response is a reaction to an overload of bacteria. The latter indicating presence of a PJI which should be treated by surgical intervention (and antibiotics), the so-called DAIR (Debridement, Antibiotics, and Implant Retention). Conversely, surgical wounds may also show prolonged leakage because of resorption of a hematoma, fatty necrosis, or anticoagulants use and take longer to heal without the need for surgery, but with the need of rest and proper wound care.

Thus, prolonged wound leakage can be interpreted as a sign of prosthetic joint infection, but according to other authors it may also be seen as a risk factor for a deep infection, since a leaking wound can be a *porte-d-entrée* for bacteria. The latter is explained by the retrograde infection pathway described by Weiss and Krackow 1993, i.e. a leaking wound can be a pathway for bacterial colonisation. Persistent wound drainage can therefore be seen as risk factor for infection or as potential imminent infection, with fluid production as reaction on the infectious process. The latter perspective would have a low threshold for performing surgical debridement and lavage [Vince 2007, Ghanem 2014]. Irrespective of the treatment modality chosen, consensus states that early adequate treatment should be started as soon as possible if a PJI is suspected [Vince 2007, Lonner 1999, Maathuis 2009, Jaber 2008, Patel 2007, Saleh 2002, Ghanem 2014]. The treatment strategies toward wound leakage vary from non-surgical treatment (bed rest, pressure bandage, wound care) to surgical treatment (DAIR). In fact, nonsurgical treatment is aimed at stopping wound leakage and DAIR is aimed at treating deep wound infection.

DAIR is meant to clean the prosthesis and the wound, and eradicate biofilm in order to conquer the infection and escape revision surgery for infection. Bacteria attached to the implant encapsulate themselves in a slime layer (biofilm), invisible to the body's innate immune response and out of reach of antibiotics [Busscher 2013]. Antibiotics do not reach the bacteria in biofilm state and only work in combination with surgery. DAIR carries a risk (probably 1-2%) of causing a new infection; it requires anaesthesia and therefore patients are subject to the regular complication risks of surgery like anaesthesia-related problems and nerve or vascular injury. It is also hypothesized that DAIR is likely executed unnecessary, as the optimal timing for a DAIR has not been proven yet. Maybe if one waits longer, the wound will heal without surgical intervention. It is generally assumed that biofilm matures within two weeks, and a mature biofilm is more difficult to eradicate. Hence theoretically, if one aims at

removing a biofilm it is best done within this term. Every intervention at an early stage is aimed at preventing major revision surgery for PJI in the future, avoiding unnecessary interventions.

Revision surgery for PJI has major implications for a patient's quality of life (multiple surgeries, longer operating times, increased blood loss and more complications, lengthy hospital stays and long-term antibiotic treatment). In addition, the costs associated with revision surgery are high (\pm € 30,000) [Kurtz, Bozicz, Vanhegan 2012]. In the Netherlands, revision surgery within one year is necessary in more than 600 patients (0.9% TKA and 1.4% THA). According to the "Landelijke Registratie Orthopedische Implantaten" (LROI), infection is the reason for revision within one year in 25.8% TKA and 12.3% THA revision cases. A Danish register study evaluated underreporting of infection as reason for revision and found it to be at least 40% [Gundtoft 2015]. This leads to the assumption that at least 1/3 of revisions within one year are related to PJI (200 patients). The associated costs for revision surgery for PJI within one year are therefore estimated at € 6,000,000 (200 x € 30,000). However, the number of revisions for PJI is probably much higher with longer follow-up, as many PJI cases are caused by lower-virulence bacteria. PJI within two years is therefore still generally considered to be related to the primary surgery. This is expressed in the LROI figures for revisions for PJI: in 2014 there were 2541 TKA and 3574 THA revisions with infection as reason for revision, 15% and 11% respectively, on a yearly base. Considering 40% underreporting, it can be estimated that approximately 1064 patients need revision surgery for PJI, of whom at least 200 are operated within the first year of index surgery and the other 800 after the first year. So it can be concluded that the actual rate of PJI is probably largely underestimated, as was also discussed for the Danish National Hip register [Gundtoft 2015]. This underestimation will also be present for the Dutch Arthroplasty register (LROI), despite its completeness of over 97% [Steenbergen 2015].

OBJECTIVES

Primary Objective:

To determine the clinical and cost effectiveness of surgical treatment (DAIR day 10) versus nonsurgical treatment in patients with wound leakage after TKA/THA.

Secondary Objective(s):

To compare the impact of surgical treatment (DAIR day 10) with nonsurgical treatment on disease-specific and general health-related quality of life.

HYPOTHESIS:

Surgical treatment (DAIR on day 10) will result in a 50% reduction rate of revision for PJI up to one year after primary TKA/THA compared to nonsurgical treatment. Consequently surgical treatment is more (cost) effective compared to nonsurgical treatment. DAIR on day 10 will result in improvement of disease-specific and general health-related quality of life compared to nonsurgical treatment.

RESEARCH QUESTION:

Primary research question

What is the clinical and cost effectiveness of surgical treatment (DAIR day 10) versus nonsurgical treatment in patients with persistent wound leakage? Primary endpoint will be revision surgery for PJI up to one year.

Secondary research questions

What is the impact of surgical treatment (DAIR day 10) compared to nonsurgical treatment on disease-specific and general health-related quality of life at one year?

2. STUDY DESIGN

A nationwide multicenter randomized controlled trial comparing surgical treatment (DAIR day 10) with nonsurgical treatment in case of persistent wound leakage after primary TKA/THA. A randomisation on patient level will be executed. The randomization procedure will be designed and implemented by the Trial Coordination Center UMCG using the validated web-based system ALEA. Each user will receive an individual login code with which to randomize patients. The web application will return the allocated treatment. As a confirmation the web application will also send an e-mail to selected users containing the randomization information. The system is online 24 hours a day, 7 days a week.

3. STUDY POPULATION

3.1 Population (base)

All patients aged 18 or older that undergo TKA/THA surgery in the participating hospitals.

3.2 Inclusion criteria

All patients aged 18 or older after primary TKA/THA surgery with a persistent wound leakage at day 9 are eligible for participation in the study.

3.3 Exclusion criteria

- Mental or physical disability to fulfil study requirements.
- Insufficient command of the Dutch language.

3.4 Sample size calculation

The power analysis is based on the assumption that, in patients experiencing persistent wound leakage at day 9, PJI eventually will develop and will necessitate revision surgery in 20% of cases. It is hypothesized that surgical intervention (DAIR day 10) will prevent 50% of PJI and consequently 50% of revision surgery for PJI in comparison to the non surgical intervention. In order to detect this 50% difference with 80% power at a significance level of 0.05, 155 patients are needed in the surgical group and 155 in the nonsurgical group. With an expected dropout rate of approximately 20% a sample size of 194 patients per group is needed (total N=388).

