7.3 Study procedures

Nonsurgical treatment

Patients in the nonsurgical treatment group will be treated following a nonsurgical treatment policy. This policy consists of relative rest (stop exercise, bed rest), wound care with sterile bandages and pressure bandage; hospital admission may be considered. On day 16 wound classification, clinical examination and CRP are performed. In case of persistent leakage at day 16, a DAIR according to study protocol is advised on days 17-20.

Surgical treatment

DAIR on day 10. DAIR is meant to clean the prosthesis and the wound in order to conquer the possibility of infection. DAIR consists of opening the wound, taking one culture from the fluid deep in the fascia and at least four deep-tissue cultures: two synovial and at least one around both components of the joint prosthesis. Only after taking cultures are antibiotics started and the hematoma and necrosis excised. Mobile parts (e.g. tibial insert, femoral

head) are exchanged to make room for optimal debridement. The wound is lavaged thoroughly with 3-6 litres of saline. Scrub sponges are used to mechanically clean all visible prosthetic parts. Povidone iodine solution or chlorhexidine solution may be used as additional intraoperative antiseptic.

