9. STATISTICAL ANALYSIS

Statistical analyses will be performed with the help of IBM SPSS statistics 22. An intention to treat analyses will be performed. For all analyses a one-tailed significant level of $p < 0.05$ is considered to be statistically significant

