9.1 Primary study parameter(s)

Clinical outcome

This study is designed as a randomized controlled trial. Every patient can be classified as nonsurgical or surgical. At least two measurements will be collected, namely before the

intervention (at day 9) and one year after the intervention. Between these two measurements additional information on the patient will be collected. The patient is also nested within a hospital, but the dependency of the measurements within the patient is our focal interest. The primary outcome of the study is revision surgery for PJI within one year (a binary variable). To take into account all these dependencies, multilevel logistic regression model with three levels will be used to analyse the data. The three levels are hospitals, patients and measurements, where measurements are nested within patients and patients are nested within hospitals. The effect of the intervention will be controlled with covariates such as age and gender.

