10.2 Recruitment and consent

All patients aged 18 or older and scheduled to undergo TKA/THA surgery in the participating hospitals will be orally informed about the LEAK study by their physician or specialised nurse when he or she is placed on the planning list for TKA/THA. In addition the patient will receive written information in the form of a flyer with background information about the study.

At the day of hospitalization all TKA/THA patients will be informed again about the study orally by the independent local research physician/nurse. On day 5-7, in case of persisting wound leakage, patients will receive a patient information letter and oral information by an independent research physician/nurse about the study and they will be asked to think about participating.

On day 9-10, patients can communicate their final decision (yes or no) to the local independent research physician/nurse with respect to participation in the study. If patients agree to participate, written informed consent will be obtained.

In case their wound is still leaking at day 9-10, they will be randomized to nonsurgical or surgical treatment.

In case the wound is dry at day 9-10, or if patients have to undergo DAIR because of high clinical suspicion for infection ($T > 38.5$, red indurated wound and pain), patients are not eligible to randomization but they can give permission to use their data for comparative analyses.

For the sake of facilitating logistics in the participating centres, consent and randomization are set at day 9 or 10; DAIR is set at day 10-11. In the general text, for easy reading, these terms are simplified to day 9 and day 10 respectively.

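### The 20% revision risk behind the sample size has no time limit, while the primary endpoint stops at one year, so the stated 80% power holds only if the whole 20% falls within that year

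*Protocol*

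**What the plan says.** The design effect in Protocol section 3.4 has two parts. The nonsurgical risk is set by the statement that in patients leaking at day 9 "PJI eventually will develop and will necessitate revision surgery in 20% of cases". The treatment effect is that DAIR on day 10 "will prevent 50% of PJI and consequently 50% of revision surgery for PJI" compared with the nonsurgical intervention. The contrast is therefore 20% versus 10%. The section continues "In order to detect this 50% difference with 80% power at a significance level of 0.05" and arrives at 155 patients per group, raised to 194 per group (388 in total) for about 20% dropout. Sidedness is given in section 9: "For all analyses a one-tailed significant level of $p < 0.05$ is considered to be statistically significant".

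The endpoint has a fixed window. Section 9.1 states: "The primary outcome of the study is revision surgery for PJI within one year (a binary variable"). The Summary, the Hypothesis and section 7.1.1 use the same one-year limit.

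The introduction (section 1) discusses timing. It expects the number of PJI revisions to be probably much higher with longer follow-up, because many infections involve low-virulence bacteria. It estimates about 1064 PJI revisions nationally, of which "at least 200 are operated within the first year of index surgery and the other 800 after the first year".

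Two other passages bear on whose risk the 20% should describe. Section 10.2 keeps patients out of randomisation "if patients have to undergo DAIR because of high clinical suspicion for infection". Section 7.3 says of the nonsurgical arm: "In case of persistent leakage at day 16, a DAIR according to study protocol is advised on days 17-20".

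**The concern.** A risk that accrues eventually and a risk that accrues within one year are different quantities, and power depends on the second. No passage says that the 20% is a one-year figure or converts it to one. The protocol also argues that revisions for PJI continue well past the first year, so the reader cannot assume that the two coincide.

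The calculation in section 3.4 is the only justification for 388 patients. Section 9.4 plans no interim analysis, so no scheduled look at the data would reveal a low event rate. If the one-year risk is well below 20%, a null result could be read as evidence against a halving of revisions when the trial had only a modest chance of detecting one.

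**Working it through.** **Inputs.** Nonsurgical risk 20%, relative reduction 50%, power 80%, significance level 0.05, 155 evaluable per arm, dropout 20% (section 3.4). One-sided testing (section 9). One-year endpoint (section 9.1).

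**Step 1: reproduce the plan's figure.** Normal approximation for two proportions with unpooled variance:

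n per arm = (z₁₋α + z₁₋β)² × [p₁(1−p₁) + p₂(1−p₂)] / (p₁−p₂)²

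One-sided 0.05: (1.645 + 0.842)² × (0.20×0.80 + 0.10×0.90) / 0.10² = 6.183 × 0.25 / 0.01 = 154.6, so 155. Dropout: 155 / 0.80 = 193.75, so 194. Both stated figures are reproduced. The two-sided version gives 196.2, so 155 is a one-sided number, in agreement with section 9.

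**Step 2: vary the one-year nonsurgical risk.** The protocol does not give this risk, so the values 15%, 10% and 5% are assumptions. The 50% reduction is kept, so p₂ = p₁/2.

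Power = Φ[(p₁−p₂)/SE − 1.645], with SE = √{[p₁(1−p₁) + p₂(1−p₂)]/n}

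At 155 per arm:
- 20% v 10%: SE = √(0.25/155) = 0.0402; 0.10/SE = 2.490; Φ(0.845) = 80%
- 15% v 7.5%: SE = √(0.196875/155) = 0.0356; 0.075/SE = 2.104; Φ(0.459) = 68%
- 10% v 5%: SE = √(0.1375/155) = 0.0298; 0.05/SE = 1.679; Φ(0.034) = 51%
- 5% v 2.5%: SE = √(0.071875/155) = 0.0215; 0.025/SE = 1.161; Φ(−0.484) = 31%

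The table adds the expected events, 155 × (p₁ + p₂), and the power if nobody drops out.

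| One-year risk, nonsurgical v surgical | Expected events, 155 per arm | Power, 155 per arm | Power, 194 per arm |
|---|---|---|---|
| 20% v 10% | 46.5 | 80% | 87% |
| 15% v 7.5% | 34.9 | 68% | 76% |
| 10% v 5% | 23.3 | 51% | 59% |
| 5% v 2.5% | 11.6 | 31% | 36% |

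A pooled-variance calculation changes these by less than one percentage point.

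**Step 3: evaluable patients needed for 80% power.** The step 1 formula gives 216.4, so 217 per arm, at 15%; 340.04, so 341, at 10%; and 711 at 5%. At a 10% one-year risk the requirement is 341/155 = 2.2 times the planned evaluable number.

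**The case against.** The best defence is that *eventually* is loose wording. The Hypothesis sets the 50% reduction at one year after the primary operation, and the endpoint sections agree, so the authors may have meant 20% at one year. That is plausible, and if so one sentence settles it. But the Hypothesis fixes the window for the relative reduction; it gives no one-year risk in the nonsurgical arm, and neither does any other passage.

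A second defence is that 155 is the floor. The plan recruits 194 per arm, and section 7.5 replaces withdrawals. This stands, and is why both columns are shown. Even with no dropout, power is below 80% at a one-year risk of 15%.

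Three stronger readings are tempting, and the document does not support them.

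- A reader might take the introduction's split and infer that only 200/1064 = 19% of revisions fall in year one, hence a one-year risk of 0.20 × 0.188 = 3.8% and power near 26%. The 1064 is derived from all hip and knee revisions in one calendar year, adjusted for underreporting, so it is a cross-section and not the time course of a cohort. The 200 is built in a different way and is stated as a lower bound. Neither concerns wounds leaking at day 9, where infection may declare itself earlier. The passage shows that the window matters; it does not supply the one-year rate.
- A reader might infer that DAIR advised on days 17-20 dilutes the contrast below 20% versus 10%. Section 3.4 defines the 50% effect against the nonsurgical intervention, and sections 4 and 7.3 include that deferred DAIR in it, so a further deduction may count it twice. The protocol gives no share of patients expected to receive it.
- A reader might infer that the section 10.2 exclusion lowers the risk among randomised patients. This is plausible, but it cannot be quantified, and the document does not say whether the 20% already allows for it.

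**Conclusion.** The point holds as a mismatch between an untimed event risk and a one-year endpoint. It is not an arithmetic error: 155 and 194 are right for the inputs used. As written, the 80% power belongs to the primary endpoint only if the entire 20% occurs within one year, which the protocol neither states nor supports and which its own remarks on later revisions call into question.

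The size depends on a figure that the protocol does not give. Under a kept 50% reduction, one-sided 0.05 and 155 evaluable per arm (194 in brackets), power is 68% (76%) at a one-year risk of 15%, 51% (59%) at 10% and 31% (36%) at 5%. None of these is an estimate of the true power. If the authors can show that 20% is the one-year risk in the randomised population, the stated power stands.

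**What to change.** In section 3.4:

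1. Replace the untimed wording with the assumed one-year risk of revision for PJI in the nonsurgical arm, and give its basis.
2. Say that this risk applies to the patients actually randomised, after the section 10.2 exclusions, and under the nonsurgical policy as written, including the DAIR advised on days 17-20.
3. State that the 50% reduction is for immediate DAIR against nonsurgical care with deferred DAIR if leakage persists.
4. Restate power for that risk, with a sensitivity range such as 5% to 20%, at both 155 and 194 per arm, naming the one-sided level. If the justified risk is lower than 20%, either revise the sample size or accept the lower power openly.

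The restatement is text only and needs no extra visits or data. Its downside is a stated power that may be less favourable. More patients would be needed only if the sponsor chose to restore 80% power at a lower risk.
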